3.4. Baseline Variables

Measurements or samples collected prior to vaccination are considered the baseline data for the assessments.

3.4.1. Demographics, Medical History and Physical Exam

The demographic variables are age at vaccination (in months for Cohort 1 and in years for Cohorts 2, 3, and 4), sex (male or female), race (Black/African American, American Indian or Alaskan native, Asian, Native Hawaiian or other Pacific Islander, White, Multiracial, and not reported), and ethnicity (Hispanic/Latino, non-Hispanic/non-Latino, and not reported). Age at vaccination for Cohort 1 will be derived in months as $12 \times (\text{vaccination date} - \text{date of birth} + 1) / 365.25$ rounded to 1 decimal place. Age at vaccination for Cohorts 2-4 will be derived in years based on the subject's birthday. For example, if the vaccination date is 1 day before the subject's 11th birthday, the subject will be considered 10 years old. For participants who did not receive a vaccine at Visit 1, the enrollment date will be used in place of the date of vaccination for the age calculation. If the Visit 1 date is also missing, then the informed consent date will be used for age calculation.

In cases where more than 1 category is selected for race, the participant will be counted under the category "Multiracial" for analysis.

Medical history will be categorized according to MedDRA.

CCI

3.4.3. Prior/Concomitant Vaccines and Concomitant Medications

Specific prior and concomitant vaccines will be collected as indicated in the protocol and recorded in the CRF. Concomitant medications will be recorded only if they are used to treat SAEs and NDCMCs. Concomitant and prior vaccines and concomitant medications will be coded using WHO DDE.

Participants' age at the time of their last 13vPnC or 7vPnC vaccination will be categorized as <1 year of age or ≥ 1 year of age. Additionally, time since the last 13vPnC or 7vPnC vaccination will be categorized in the following intervals: 2 to <6 months, 6 to <12 months, 1 to <5 years, 5 to <10 years, and 10 years or more.

3.5. Safety Endpoints

Local reactions, systemic events, antipyretic/pain medication, AEs, SAEs, and NDCMCs have been described above in the primary endpoints.

4. ANALYSIS SETS (POPULATIONS FOR ANALYSIS)

Analysis populations are defined for the statistical analysis of safety and immunogenicity results in the table below.

Population	Description
Enrolled	All participants who have a signed ICD.
Evaluable immunogenicity	All participants who: 1. Are eligible, 2. Receive 20vPnC, 3. Have at least 1 valid immunogenicity result from 1 month after vaccination collected within 27 to 56 days after vaccination for Cohorts 1-2 or within 27 to 49 days after vaccination for Cohorts 3-4, and 4. Have no other major protocol deviations as determined by the clinician The evaluable immunogenicity population will be used as the primary analysis population for the pneumococcal immunogenicity results.
CCI	[REDACTED]
Safety	All participants who receive 20vPnC and have safety follow-up after vaccination.

PFIZER GENERAL BUSINESS

[REDACTED]

For the evaluable immunogenicity population definition, the blood collection window has been expanded by 1 extra day before and 14 days after the protocol-specified blood collection window of 28 to 42 days, for consistency with established rules in the Prevnar 13® development program for Cohorts 1 and 2. For Cohorts 3 and 4, the window was expanded by 1 day before and 7 days after the protocol-specified blood collection window consistent with the 20vPnC adult program. A major protocol deviation is a protocol deviation that, in the opinion of the Pfizer clinician or medical monitor, would materially affect assessment of immunogenicity, eg, participant receipt of a prohibited vaccine or medication that might affect immune response or a medication error with suspected decrease in potency of the vaccine.

CC1

E-diary data will be summarized among those in the safety population who report any e-diary data.

5. GENERAL METHODOLOGY AND CONVENTIONS

5.1. Hypotheses and Decision Rules

5.1.1. Cohort 1 and Cohort 2

For the primary immunogenicity objective, hypothesis testing will be used to assess superiority of the IgG concentrations for the 7 additional pneumococcal serotypes 1 month after 20vPnC to the IgG concentrations before 20vPnC within each cohort. The null hypothesis (H_0) for a serotype is

$$H_0: \mu_{\text{fold rise}} \leq 1.0$$

where

- $\mu_{\text{fold rise}}$ is the geometric mean of the fold rise in IgG concentration from before to 1 month after vaccination;

The null hypothesis (H_0) will be rejected for a serotype if the lower bound of the 2-sided 95% CI calculated based on the Student's t-distribution ([Section 5.2.2.2](#)) for the IgG GMFR is greater than 1.0.

5.1.2. Cohort 3 and Cohort 4

For the primary immunogenicity objective, hypothesis testing will be used to assess superiority of the OPA titers for the 7 additional pneumococcal serotypes 1 month after 20vPnC to the OPA titers before 20vPnC within each cohort. The null hypothesis (H_0) for a serotype is

$$H_0: \mu_{\text{fold rise}} \leq 1.0$$

where

- $\mu_{\text{fold rise}}$ is the geometric mean of the fold change in OPA titer from before to 1 month after vaccination;

The null hypothesis (H_0) will be rejected for a serotype if the lower bound of the 2-sided 95% CI calculated based on the Student's t-distribution ([Section 5.2.2.2](#)) for the OPA GMFR is greater than 1.0.

5.2. General Methods

Safety and immunogenicity results will be summarized separately for each cohort.

Time points for local reactions and systemic events refer to data within 7 days after vaccination.

CIs for all endpoints in the statistical analysis will be presented as 2-sided at the 95% level.

5.2.1. Analyses for Binary Endpoints

Descriptive statistics for categorical variables (eg, proportions) are the percentage (%), the numerator (n), and the denominator (N) used in the percentage calculation, with 95% CIs.

The exact 95% CI for binary endpoints for each group will be computed using the F distribution (Clopper-Pearson).²

5.2.2. Analyses for Continuous Endpoints

Unless otherwise stated, descriptive statistics for continuous variables are n, mean, median, standard deviation, minimum, and maximum.

5.2.2.1. Geometric Mean

For immunogenicity results of serotype-specific IgG concentrations and OPA titers, the GM will be computed along with associated 95% CIs. The GM and associated 2-sided 95% CI will be calculated as the mean of the assay results on the natural logarithmic scale based on the Student's t-distribution, and then exponentiating the results.

5.2.2.2. Geometric Mean Fold Rises

The GMFRs will be calculated by exponentiating the mean of the difference of logarithmically transformed assay results (later minus earlier). The associated 2-sided 95% CIs are computed by exponentiating the limits of CIs obtained using the Student's t-distribution for the mean difference on the natural log scale.

CCI

5.3. Methods to Manage Missing Data

A partial AE start date (missing day or missing both month and day) will be imputed by assigning the earliest possible start date using all available information, such as the stop date of the AE and the vaccination date(s) from the same participant, following the Pfizer standard of handling incomplete AE start date. A complete missing start date for an AE is not allowed in the data collection.

Methods for handling missing local reactions and systemic events data are described in [Section 3.1.1.1](#) and [Section 3.1.1.2](#), respectively.

The LLOQ for each assay will be provided by Vaccines Research and Development as part of the electronic data transfer or within the Clinical Testing Completion Memo prior to statistical analysis. Assay results above the LLOQ will be reported, and values below the LLOQ, denoted as BLQ, will be imputed as $0.5 \times \text{LLOQ}$ for analysis.

No additional imputation will be applied to other missing data.

6. ANALYSES AND SUMMARIES

6.1. Primary Endpoint(s)

6.1.1. Primary Safety Endpoint(s)

6.1.1.1. Local Reactions

6.1.1.1.1. Main Analysis

- Estimand: The percentage of participants reporting prompted local reactions (redness, swelling, and pain at the injection site) within 7 days after vaccination (Section 2.1).
- Analysis set: Safety population (Section 4).
- Analysis time point: Within 7 days after vaccination.
- Analysis methodology: Descriptive statistics.
- Intercurrent events and missing data: Missing values will not be imputed. CCI
- Reporting results: Count and percentage of participants with the indicated endpoint and the associated 2-sided 95% CI for each and any local reaction after vaccination in each cohort will be presented by maximum severity across severity levels.

CCI

PFIZER GENERAL BUSINESS

CCI

[REDACTED]

6.1.1.2. Systemic Events

6.1.1.2.1. Main Analysis

- Estimand: The percentage of participants reporting prompted systemic events (Cohort 1: fever, decreased appetite, irritability, and drowsiness/increased sleep; Cohorts 2-4: fever, fatigue, headache, muscle pain, and joint pain) within 7 days after vaccination (Section 2.1).
- Analysis set: Safety population (Section 4).
- Analysis time point: Within 7 days after vaccination.
- Analysis methodology: Descriptive statistics.
- Intercurrent events and missing data: Missing values will not be imputed. CCI [REDACTED]
- Reporting results: Count and percentage of participants with the indicated endpoint and the associated 2-sided 95% CI for each and any systemic event after vaccination in each cohort will be presented by maximum severity across severity levels.

CCI

[REDACTED]

[REDACTED]

[figure not shown]
[REDACTED]

[REDACTED]

[REDACTED]

PFIZER GENERAL BUSINESS

CCI

6.1.1.3. Adverse Events

6.1.1.3.1. Main Analysis

- Estimands: The percentages of participants reporting AEs from vaccination to 1 month after vaccination ([Section 2.1](#)).
- Analysis set: Safety population ([Section 4](#)).
- Analysis time points: Vaccination to 1 month after vaccination.
- Analysis methodology: Descriptive statistics.
- Intercurrent events and missing data: No missing values will be imputed except for partial AE start dates ([Section 5.3](#)).
- Reporting results: The numerator (n) and the denominator (N) used in the percentage calculation, the percentage (%), and the corresponding 2-sided 95% CI for participants reporting any AE, by each system organ class and each preferred term within system organ class, will be presented by cohort.

CCI

6.1.1.4. Serious Adverse Events and Newly Diagnosed Chronic Medical Conditions

6.1.1.4.1. Main Analysis

- Estimands:
 - The percentage of participants reporting SAEs from vaccination to 6 months after vaccination ([Section 2.1](#)).
 - The percentage of participants reporting NDCMCs from vaccination to 6 months after vaccination ([Section 2.1](#)).
- Analysis set: Safety population ([Section 4](#)).
- Analysis time points: Vaccination to 6 months after vaccination.
- Analysis methodology: Descriptive statistics.
- Reporting results: The numerator (n) and the denominator (N) used in the percentage calculation, the percentage (%), and the corresponding 2-sided 95% CI for participants reporting any SAEs/NDCMCs, by each system organ class and each preferred term within system organ class, will be presented by cohort. SAEs and NDCMCs will be presented separately.

CCI

6.1.2. Primary Immunogenicity Endpoint(s)

The ordering of the pneumococcal serotypes in summaries displaying only the 7 additional serotypes will be as follows:

- 8, 10A, 11A, 12F, 15B, 22F, and 33F.

6.1.2.1. IgG Concentration

6.1.2.1.1. Main Analysis

[figure not shown]
- Estimands: For Cohorts 1 and 2, GMFRs of pneumococcal serotype-specific IgG concentrations for the 7 additional serotypes from before to 1 month after vaccination ([Section 2.1](#)).
- Analysis set: Evaluable immunogenicity population ([Section 4](#)).
- Analysis time points: Before and 1 month after vaccination.
- Analysis methodology: The GMFR and corresponding 2-sided 95% CI will be calculated as described in [Section 5.2.2.2](#). Superiority will be declared if the lower bound of the 95% CI is greater than 1.0.
- Intercurrent events and missing data: Serology data deemed unevaluable because of noncompliance with the key protocol criteria will be excluded. Missing data will not be imputed.
- Reporting results: For each of the 7 additional vaccine serotypes, the GMCs, the GMFRs, and the corresponding 2-sided 95% CIs will be presented for each cohort at the specified time points.

6.1.2.2. OPA Titers

6.1.2.2.1. Main Analysis

- Estimands: For Cohorts 3 and 4, GMFRs of pneumococcal serotype-specific OPA titers for the 7 additional serotypes from before to 1 month after vaccination ([Section 2.1](#)).
- Analysis set: Evaluable immunogenicity population ([Section 4](#)).
- Analysis time points: Before and 1 month after vaccination.
- Analysis methodology: The GMFR and corresponding 2-sided 95% CI will be calculated as described in [Section 5.2.2.2](#). Superiority will be declared if the lower bound of the 95% CI is greater than 1.0.
- Intercurrent events and missing data: Serology data deemed unevaluable because of noncompliance with the key protocol criteria will be excluded. Missing data will not be imputed.
- Reporting results: For each of the 7 additional vaccine serotypes, the GMTs, the GMFRs, and the corresponding 2-sided 95% CIs will be presented for each cohort at the specified time points.

PFIZER GENERAL BUSINESS

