- **Cohort 1:** Approximately 200 children ≥ 15 months to <24 months (<2 years) of age who have been previously vaccinated with at least 3 doses of 13vPnC.
- **Cohort 2:** Approximately 200 children ≥ 2 years to <5 years of age who have been previously vaccinated with at least 3 doses of 13vPnC.
- **Cohort 3:** Approximately 200 children ≥ 5 years to <10 years of age regardless of documentation of previous vaccination with 7vPnC or 13vPnC.
- **Cohort 4:** Approximately 200 children ≥ 10 years to <18 years of age regardless of documentation of previous vaccination with 7vPnC or 13vPnC.

Duration of Participation for Each Participant

Each participant will participate in the study for approximately 6 months.

PFIZER CONFIDENTIAL

CCI

Statistical Methods

The primary safety objective will be evaluated by descriptive summary statistics for local reactions, systemic events, and AEs, including SAEs and NDCMCs, for each age cohort.

The primary immunogenicity objectives will be evaluated by formal hypothesis tests for superiority of IgG concentrations for the 7 additional serotypes (8, 10A, 11A, 12F, 15B, 22F, and 33F) 1 month after 20vPnC to before 20vPnC in Cohorts 1 and 2, and superiority of OPA titers for the 7 additional serotypes 1 month after 20vPnC to before 20vPnC in Cohorts 3 and 4. Superiority for a serotype in each cohort will be declared if the lower bound of the 2-sided 95% confidence interval (CI) for the IgG (or OPA) GMFR from before 20vPnC to 1 month after 20vPnC for that serotype is greater than 1.

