9.1.2. Statistical Hypotheses

9.1.2.1. Cohort 1 and Cohort 2

For the primary immunogenicity objective, hypothesis testing will be used to assess superiority of the IgG concentrations for the 7 additional pneumococcal serotypes 1 month after 20vPnC to the IgG concentrations before 20vPnC within each cohort. The null hypothesis (H_0) for a serotype is

$$H_0: \mu_{\text{fold-rise}} \leq 1.0$$

where

- $\mu_{\text{fold-rise}}$ is the geometric mean of the fold rise in IgG concentration from before to 1 month after vaccination;

The null hypothesis (H_0) will be rejected for a serotype if the lower bound of the 2-sided 95% CI for the IgG GMFR is greater than 1.0.

9.1.2.2. Cohort 3 and Cohort 4

For the primary immunogenicity objective, hypothesis testing will be used to assess superiority of the OPA titers for the 7 additional pneumococcal serotypes 1 month after 20vPnC to the OPA titers before 20vPnC within each cohort in a randomly selected subset of participants. The null hypothesis (H_0) for a serotype is

$$H_0: \mu_{\text{fold-rise}} \leq 1.0$$

where

- $\mu_{\text{fold-rise}}$ is the geometric mean of the fold change in OPA titer from before to 1 month after vaccination;

The null hypothesis (H_0) will be rejected for a serotype if the lower bound of the 2-sided 95% CI for the OPA GMFR is greater than 1.0.

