9.1.3. Multiplicity Considerations

The primary immunogenicity objectives for superiority are evaluated separately for each cohort. Within each cohort, superiority of the immune response 1 month after 20vPnC to before vaccination (serotype-specific IgG concentrations for Cohorts 1 and 2; serotype-specific OPA titers for Cohorts 3 and 4) is assessed by the hypothesis tests as described in Section 9.1.2.1 or Section 9.1.2.2, each hypothesis test at an alpha level of 0.05 for each serotype. The primary immunogenicity objectives will be achieved if the superiority of the immune response 1 month after 20vPnC to before 20vPnC is established for all 7 additional serotypes in a given cohort. Therefore, the overall type I error rate for immunogenicity evaluation is well controlled at the 0.05 level for each cohort.

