9.4.1. Immunogenicity Analyses

The statistical analysis of pneumococcal immunogenicity results will be primarily based on the evaluable immunogenicity population as defined in [Section 9.3](#). [CCI](#)

CCI

CCI

Participants will be summarized according to the vaccine group as randomized. Missing serology data will not be imputed.

Endpoint	Statistical Analysis Methods
Primary	
 Pneumococcal serotype-specific IgG GMFRs from before to 1 month after 20vPnC 
For each of the 20 serotypes in each cohort, GMFRs and the associated 95% CIs for serotype-specific IgG concentrations from before to 1 month after vaccination will be provided. The GMFR will be calculated by exponentiating the mean of the difference of logarithmically transformed assay results (1 month after vaccination – before vaccination for each participant). Two-sided CIs will be obtained by calculating the CIs using Student's t-distribution for the mean difference of measures on the logarithmically transformed assay results and exponentiating the limits.
 
In Cohort 1 and Cohort 2, for each of the 7 additional serotypes, the lower limit of the 2-sided 95% CI of the IgG GMFR for a serotype will be used in the hypothesis test for superiority of IgG concentrations 1 month after 20vPnC to before 20vPnC for that serotype, as detailed in Section 9.1.2.1.

Endpoint	Statistical Analysis Methods
	
 Pneumococcal serotype-specific OPA GMFRs from before to 1 month after 20vPnC For each of the 20 serotypes in each cohort, GMFRs of OPA titers from before vaccination to 1 month after vaccination will be analyzed the same way as the IgG GMFRs. In Cohort 3 and Cohort 4, for each of the 7 additional serotypes, the lower limit of the 2-sided 95% CI of the OPA GMFR for a serotype will be used in the hypothesis test for superiority of OPA titers 1 month after 20vPnC to before 20vPnC for that serotype, as detailed in Section 9.1.2.2.

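### Does the SAP's serotype-by-serotype superiority rule undo the protocol's 0.05 error control per cohort?

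*SAP*

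**What the plan says.** Protocol 9.1.2 sets, for each additional serotype in each cohort, the null hypothesis that the geometric mean fold rise (GMFR) is at most 1.0. The measure is IgG in Cohorts 1 and 2 and OPA titer in Cohorts 3 and 4. For IgG the null "will be rejected for a serotype if the lower bound of the 2-sided 95% CI for the IgG GMFR is greater than 1.0", and OPA has a matching sentence.

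Protocol 9.1.3 puts "each hypothesis test at an alpha level of 0.05 for each serotype". It treats the objective as achieved when superiority "is established for all 7 additional serotypes in a given cohort", and concludes: "Therefore, the overall type I error rate for immunogenicity evaluation is well controlled at the 0.05 level for each cohort".

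Other places speak of one serotype at a time:

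- Protocol synopsis: "Superiority for a serotype in each cohort will be declared if the lower bound of the 2-sided 95% confidence interval" for the GMFR lies above 1.
- SAP 5.1: "The null hypothesis (H_0) will be rejected for a serotype if the lower bound of the 2-sided 95% CI", based on the t-distribution, exceeds 1.0.
- SAP 6.1.2.1.1 and 6.1.2.2.1: "Superiority will be declared if the lower bound of the 95% CI is greater than 1.0".

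SAP 5.1 and 6.1.2 contain no all-seven condition and no multiplicity text. Protocol Section 9 and SAP Section 2 both allow the SAP to depart from the protocol. Both add that a major change to the primary endpoint definition or its analysis will also be reflected in a protocol amendment.

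**The concern.** Unadjusted testing of seven hypotheses is justified here only by the requirement that all seven succeed. That logic protects the joint claim and nothing else. The SAP section on hypotheses and decision rules carries over the protocol's hypotheses but not the success criterion, and both documents use the language of declaring superiority for single serotypes.

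Neither document says what may be claimed if six of seven pass, and such an outcome is foreseeable. In Protocol Table 6, 11A passes with probability 64% under Assumption 1 and 91% under Assumption 3. If six passing serotypes were then reported as stand-alone confirmatory findings, the 0.05 control would not cover them.

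The stated alpha also looks inconsistent, because a one-sided null rejected on the lower limit of a 2-sided 95% interval is tested at 0.025, not 0.05.

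**Working it through.** **Inputs.** Seven tests per cohort (Protocol 9.4.1, "for each of the 7 additional serotypes"); rejection when the lower limit of the 2-sided 95% CI exceeds 1.0, so one-sided level 0.025 (Protocol 9.1.2, SAP 5.1); powers from Protocol Table 6. The correlation between serotype tests is not given and is varied below as an assumption.

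**1. The level Table 6 uses.** One-sample t-test power on the log scale is 1 − F(t(1−α, n−1); n−1, δ√n), with F the noncentral t distribution.

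- With α = 0.025, 64% at n = 90 for 11A gives δ = 0.247. At n = 180 the power is then 90.9%; the protocol states 91%.
- With α = 0.05 one-sided, the same steps give 88.5%, which does not match.

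The operative level is one-sided 0.025. Calling it 0.05 is ordinary two-sided labelling.

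**2. The criterion Table 6 uses.** Under Assumption 1, treating the tests as independent and the other five serotypes as near certain, 11A and 33F give 0.64 × 0.98 = 0.627. The Overall row states 63%. The trial's power is therefore computed for passing all seven, in line with Protocol 9.1.3.

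**3. Error for the cohort objective.** A false claim of success requires rejecting every null, including at least one true null j. So P(reject all 7) ≤ P(reject j) ≤ 0.025, for any correlation. This is inside the stated 0.05.

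**4. Error if single-serotype declarations stood alone.** With k true nulls and independent tests, P(at least one false declaration) = 1 − 0.975^k:

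| True nulls k | 1 | 2 | 3 | 7 |
|---|---|---|---|---|
| Chance | 2.5% | 4.9% | 7.3% | 16.2% |

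For k = 7 the Bonferroni bound is 7 × 0.025 = 17.5%. With equal correlation the k = 7 figure is 13.7% at 0.3, 11.5% at 0.5, 8.9% at 0.7 and 5.7% at 0.9. It falls below 5% only above a correlation of about 0.93.

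**5. What an 11A miss means.** Its chance is 100 − 64 = 36% under Assumption 1 (n = 90) and 100 − 91 = 9% under Assumption 3 (n = 180). SAP 3.2 has the seven additional serotypes assayed for OPA in all Cohort 3 and 4 participants, and the target is 180 evaluable per cohort. At the same assumed GMFR, Assumption 3 is therefore the relevant one.

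Both scenarios assume a true 11A GMFR above 1. Back-solving from the rounded 64% and 95% entries gives about 1.7 at the 75% assumption. The other six serotypes have power of at least 98%, so their fold rises are real as well. An 11A miss in this setting is a false negative, and the six remaining declarations are true. For Cohorts 1 and 2 every Table 6 entry, including Overall, is above 99%.

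**The case for a change.** The best case for a change is that the decision-rules section of a SAP should state what counts as success. This one reproduces the protocol's hypotheses without the criterion that justifies unadjusted testing. Because the SAP is allowed to modify the protocol, a reader might not be able to tell oversight from intent. A partial result is also plausible: with 91% power in each of Cohorts 3 and 4 and independence between them, the chance that at least one misses is 1 − 0.91² = 17%. The repair would cost a few sentences.

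Two parts of this stand. The SAP does omit the criterion, and the per-cohort control does not extend to serotype claims made on their own.

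The inference to a defect does not stand. Dropping the all-seven condition would be a major change to the primary analysis, which both documents say will appear in a protocol amendment. The SAP announces no such change. The serotype wording also has a necessary job, because superiority for one serotype must be defined before it can be required of seven. Relabelling alpha as one-sided 0.025 would leave the rejection rule exactly as it is.

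The stronger remedies are matters of preference. Withholding every serotype-level statement after one miss would suppress results that are probably true. Bonferroni for stand-alone claims would cut 11A power from 64% to about 35%, from 95% to about 81% and from 91% to about 72% under Assumptions 1, 2 and 3. Holm would cost much less, but where the other six pass comfortably it would mostly return the same declarations as the present rule.

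**Conclusion.** No change is needed. The SAP omission is a gap that an analyst fills from Protocol 9.1.3: a cohort succeeds if all seven lower limits exceed 1.0, and the serotype results are components of that decision. For that decision the type I error is at most 0.025, so the protocol's 0.05 statement is correct and conservative. Repeating the criterion in the SAP would be tidy but would change no estimate, interval, power figure or cohort-level conclusion.

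The 16.2% is a worst case that needs seven ineffective conjugates and independent tests. With one or two true nulls the chance of a false serotype claim stays below 5% under independence.

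The conclusion assumes that the protocol criterion still governs and that a cohort missing one serotype is reported as not having met its objective.
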